### ***Potential for Benefit***

Our study proposing the Ga-citrate PET/CT imaging will aid in management of prosthetic infections in many different ways. Currently, Ga-citrate is not approved by Food and Drug Administration (FDA). Data obtained from this pilot study will aid in obtaining extramural funding to conduct a large-scale human study that may pave a road for obtaining FDA approval to use Ga-citrate for clinical purpose. Routine clinical use of Ga-citrate PET/CT imaging will aid in differentiating periprosthetic infection from aseptic loosening. As explained above, currently available imaging modalities including FDG PET/CT have poor capability for this differentiation. Ga-citrate PET/CT by the mean of its functional nature has the potential to overcome this shortage in patient care.

#### **4. Statistical Analysis:**

For each subject, we will record the presence and location of abnormal uptake. For the PET/CT images, we will generate a region-of-interest (ROI) around each area of morphologic abnormality to calculate a mean standardized uptake value (SUV), a maximum SUV, and a target-to-background ratio. A target-to-background ratio of at least 2.0 will be used to score a particular ROI as positive. These values will be compared quantitatively with those of contralateral normal joint. Radiotracer uptake pattern on each modality will be classified according to known methods (29). Then, we will descriptively and quantitatively correlate Ga-citrate PET/CT findings with those of F-FDG PET/CT. Using the macroscopic intraoperative and later tissue histology and culture as the gold standard, sensitivity, specificity, and positive and negative predictive values of Ga and FDG PET will be calculated and compared with each other. We will also review the PET/CT images for multifocal involvement, if any.

#### **Statistical Analysis:**

Primarily, all variables will be analyzed and overall, descriptively, as follows:

- Mean, standard deviation, median and range for continuous variables
- Median, range and frequency distribution for discrete (ordinal) variations

- The results of the imaging modalities (PET, CT and MRI) will be classified as true positive (TP), true negative (TN), false positive (FP), or false negative (FN) according to the reference standard.
- The McNemar test of correlated properties will be used to statistically compare the imaging results of Ga-citrate and F-FDG PET with MRI and diagnostic CT.
- The student t-test will be used to statistically compare the quantitative findings of Ga-citrate and F-FDG scans.
- Analysis will be done on a lesion basis and on a patient basis.
- All P values, <0.05 will be considered significant.
- Cohen's k-statistic with 95% confidence intervals will be calculated to show the degree of association between the techniques.

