**Study Title: Novel Gallium 68 Citrate Imaging in Orthopedic Infections.**

**Principal Investigator: [name]**

**Study Site: Rutgers New Jersey Medical School**

**1. Purpose/Specific Aims:**

The purpose of the current study is to demonstrate the feasibility and evaluate the accuracy of Gallium (Ga)-citrate positron emission tomography/computed tomography (PET/CT) in diagnosing prosthetic joint infection and compare it with fluorine-fluorodeoxyglucose-positron emission tomography/computed tomography (FDG-PET/CT). We expect that Ga-citrate PET/CT will serve as a novel molecular-based sensitive functional imaging modality superior to FDG-PET/CT. We intend to translate the results of this preliminary study to fuel larger studies in the utility of Ga-citrate PET/CT to evaluate prosthesis complications, where current available imaging techniques are challenging.

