**2. Background and Significance**

**Epidemiology:**

A total of 4.5 and 6.7 million people in the United States are currently living with an artificial hip or knee. With aging of the population, and increased obesity and longevity, this number is likely to increase in the coming decades and will create significant challenges for management of long-term complications (1). The local complications of joint replacement include infection, instability and dislocation, aseptic loosening and periprosthetic fracture. Periprosthetic infection, the most devastating complication of joint replacement, is associated with significant morbidity and cost. The infection rates following primary implantation and revision surgery are approximately 1% and 3% for hip prostheses and 2% and 5% for knee prostheses, respectively (2, 3). The most common complication, on the other hand, is aseptic loosening which is most often caused by wear of the prosthetic components. For hip replacement, the risk of aseptic loosening leading to revision total hip arthroplasty is about 1 percent per year (4). It is crucial to differentiate prosthetic joint infection from aseptic loosening for appropriate patient management. The treatment for prosthesis infection generally involves both systemic antibiotics for an extended period and exchange arthroplasty in one or two stages, whereas aseptic loosening usually requires a single revision arthroplasty (5, 6).

Physical examination, laboratory tests, radiography and joint aspiration used to diagnose prosthesis infection are insensitive and/or nonspecific. Evaluation of prosthetic joint with morphologic imaging such as CT or MRI has been plagued by poor differentiation between infection and aseptic inflammation/loosening. These modalities are also hampered by artifacts produced by the prosthetic devices themselves (2). Functional modalities have the ability to detect infection when morphologic imaging is nonspecific (2, 7). Of these modalities, promising data exist

supporting combined leukocyte–marrow scintigraphy, 67Gallium (67Ga)-citrate imaging and 18fluorine-fluorodeoxyglucose-positron emission tomography (FDG-PET).

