### **F-FDG-PET:**

FDG acts as a glucose analog and is taken up by metabolically active cells, namely leucocytes, neutrophilic granulocytes, and macrophages because of increased glucose metabolism and expression of glucose transporters in these cells. In the case of infection, it is also taken up by bacteria present in the infected tissue (9-12). This increased FDG uptake makes local detection of bacterial infections possible. Although FDG PET/CT has high diagnostic sensitivity to detect prosthetic joint infection, its specificity is low, that is, it fails to differentiate between prosthesis infection and aseptic loosening (7, 8, 10, 13-20). The presence of periprosthetic FDG uptake in a non-infected prosthesis can be explained by altered marrow distribution secondary to the placement of an orthopaedic prosthesis (15) and an immunological reaction to wear-induced polyethylene and metal particles released from the prosthesis inlay (7).

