### **Preliminary Studies:**

Gallium labeled radiotracers are extensively researched in Europe, Asia and Africa. However, research in this area in United States is lagging behind due to lack of commercially available generator. In preliminary studies,  $^{68}\text{Ga}$ -citrate PET/CT has been successful to identify soft tissue cellulitis and abscess in humans and osteomyelitis in animal models (21). In animal models of *Staphylococcus aureus* infection, Kumar et al demonstrated avid uptake of  $^{68}\text{Ga}$ -citrate at infected lesions as early as 5 min following injection. Despite concomitant decrease in cardiac blood pool activity, the radiotracer uptake continued to increase for up to 6 h post injection (26).  $^{68}\text{Ga}$ -citrate PET/CT has been shown to be superior to FDG PET in differentiating early bone healing from osteomyelitis in rats (12). To the best of our knowledge, there is only a single human study from Italy aiming to evaluate the efficacy of  $^{68}\text{Ga}$ -citrate PET/CT in patients with acute osteomyelitis, chronic osteomyelitis, or diskitis (27). Although a small number of patients (4 of 31) were found to have false-positive scans, the authors reported a sensitivity of 100%, a specificity of 76%, and overall accuracy of 90% in identifying these patients' sites of infection. However, regarding periprosthetic infection, their study was limited due to availability of only 7 patients with bone implants (not necessarily prosthesis) and lack of comparison with FDG PET/CT. With this background, we aim to demonstrate the feasibility and evaluate the accuracy of  $^{68}\text{Ga}$ -citrate PET/CT in diagnosing prosthetic joint infection, and compare the results with those of FDG PET for the first time.

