#### ***Population characteristics:***

**Record Selections:** The following data will be obtained from the charts of the index cases:

1. Age
2. Gender
3. Race/ethnicity

4. Past Medical History
5. Past surgical history
6. Current medications
7. Prior medications
8. Weight, height and body mass index
9. History of alcohol abuse
10. History of intravenous drug use
11. Evidence of HIV infection (e.g. HIV RNA/DNA PCR, Western blot, viral load)
12. History of any other joint, connective tissue or systemic inflammatory diseases (e.g. systemic lupus erythematosus, sarcoidosis, amyloidosis)
13. Joint replacement postoperative course
14. White blood cell count
15. Erythrocyte sedimentation rate
16. C-reactive protein level
17. Histopathology for any biopsied joint/bone tissue
18. Pre and postoperative CT/MRI

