### **Image Acquisition Parameters:**

**Gallium PET/CT:**  $^{68}\text{Ga}$ -citrate will be synthesized according to the method described in the literature (28). IBA Molecular, a commercial radiopharmacy, will obtain a  $^{68}\text{Ge}/^{68}\text{Ga}$  generator that is produced by ITG Isotope Products. The IBA Molecular radiopharmacy will synthesize  $^{68}\text{Ga}$ -citrate and deliver to our facility in unit doses. Technologists will establish the intravenous access and the subject will receive 5 mCi of  $^{68}\text{Ga}$ -citrate intravenously. The subject will be placed in uptake room for 60 minutes to allow for optimal localization of investigational compound. Whole body PET/CT scan will be performed after 60 minutes of uptake phase.

Combined PET/CT imaging will be performed using the Discovery LS scanner (GE Medical Systems, Waukesha, WI). The CT scanner portion of the Discovery LS consists of a multi-detector helical CT (GE Lightspeed Plus, Waukesha, WI).

- Low dose CT scan will be performed followed by positron emission scan.
- CT imaging parameters will be as follows for a 6 to 7 bed position acquisition: 140 kVp, 80 mA, 0.8 s per CT rotation, pitch of 6, 22.5 mm/s table speed. CT thickness will be 5 mm.
- Positron emission data will be acquired for two sets of 6 positions, one starting from vertex to mid-thigh level and the second from pelvis to toes. Emission data will be acquired for 5 minutes for each bed position.
- PET images will be reconstructed using CT for attenuation correction with the ordered subset expectation maximization (OSEM) algorithm.

**FDG PET/CT:** Subjects will undergo FDG PET/CT scan using the same imaging parameters either on the same day or within the next 24-48 hours. The IBA Molecular radiopharmacy will synthesize F-FDG and deliver to our facility in unit doses. The subjects will be requested to fast for a minimum of 4 h prior to PET acquisition. After confirmation of a blood glucose level  $\leq$ 200 mg/dl, technologists will establish the intravenous access and the subject will receive approximately 10 mCi of F-FDG intravenously. The subject will be placed in uptake room for 60 minutes to allow for optimal localization of the compound. subjects will be requested to void prior to administration of 18FDG and again prior to image acquisition. Whole body PET/CT scan will be performed after 60 minutes of uptake phase using similar imaging parameters as described above.

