***Data analysis:***

For each subject, we will record the presence and location of abnormal uptake on both Ga and FDG PET/CTs. We will then generate a region-of-interest around each area of morphologic abnormality to calculate a mean standardized uptake value (SUV), a maximum SUV, and a target-to-background ratio. These values will be compared with those of contralateral normal joint. Radiotracer uptake pattern on each modality will be classified according to known methods (29). Using the macroscopic intraoperative and later tissue histology and culture as the gold standard, sensitivity, specificity, and positive and negative predictive values of Ga and FDG PET will be calculated and compared with each other.

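### The plan promises to compare Ga and FDG accuracy but names no paired difference, interval or test for it; its only paired categorical test is worded against MRI and diagnostic CT taken from charts

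*Protocol*

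**What the plan says.** - **Aim.** Protocol section 1 and the opening of the SAP set out to evaluate Ga-68 citrate PET/CT and compare it with FDG PET/CT. They expect that Ga "will serve as a novel molecular-based sensitive functional imaging modality superior to FDG-PET/CT". Protocol section 3 gives both scans to each of 17 subjects.
- **Promised comparison.** Protocol section 3 (Data analysis) says that "sensitivity, specificity, and positive and negative predictive values of Ga and FDG PET will be calculated and compared with each other". Protocol section 4 repeats the sentence, and so do both descriptive paragraphs of the SAP. None of the four places names a method.
- **Named methods.** The bulleted lists in Protocol section 4 and in the SAP have the same content. Imaging results are classed as true or false positive or negative against the reference standard. McNemar is used to "statistically compare the imaging results of 68 Ga-citrate and 18 F-FDG PET with MRI and diagnostic CT". A Student t-test compares the quantitative findings of the two tracers. Cohen's kappa, with a 95% CI, describes association between techniques. P below 0.05 is significant.
- **Source of MRI and CT.** The chart-abstraction list in Protocol section 3 (Population characteristics) ends with "Pre and postoperative CT/MRI". The imaging sections schedule no MRI or diagnostic CT. The study's own CT is the one in "Low dose CT scan will be performed followed by positron emission scan", used for attenuation correction.

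**The concern.** The design is paired and the question is Ga against FDG, yet the one paired test in the list names other comparators. Those comparators are not study procedures, and no timing or completeness rule governs them. The protocol's background already regards them as weak: "Evaluation of prosthetic joint with morphologic imaging such as CT or MRI has been plagued by poor differentiation between infection and aseptic inflammation/loosening". Doing better than MRI or CT would not show that Ga is better than FDG.

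Followed literally, the bullets give a comparison with MRI/CT, a comparison of uptake and an agreement coefficient. The promised comparison of accuracy would have no stated estimate of the Ga-FDG difference and no measure of its uncertainty. That difference, with its interval, is the most useful thing a pilot can hand to the larger study it is meant to support.

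Sensitivity and specificity must also be kept apart, because the protocol expects the gain in one of them: "Although FDG PET/CT has high diagnostic sensitivity to detect prosthetic joint infection, its specificity is low".

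**Working it through.** **1. Which named method answers the question?**

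| Method | What it compares | Uses the reference standard? | Ga-FDG accuracy difference with interval? |
|---|---|---|---|
| McNemar, as worded | Each tracer with MRI and diagnostic CT | Yes, if results are scored TP/TN/FP/FN | No |
| t-test | Uptake values of the two tracers | No | No |
| Kappa with 95% CI | Agreement between techniques | No | No |
| TP/TN/FP/FN classification | Each modality with the reference | Yes | Supplies the data only |

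The plan gives no power, effect size or precision figure for N = 17, so there is no figure of its own to reproduce.

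**2. Can kappa stand in?** Inputs: N = 17 (documents); 9 infected and 8 aseptic (assumed, since no prevalence is given); both tracers positive 11, FDG only 3, Ga only 0, neither 3 (illustration).

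- Observed agreement: (11 + 3)/17 = 0.824.
- Chance agreement: Ga is positive in 11 and FDG in 14, so (11×14 + 6×3)/17² = 172/289 = 0.595.
- Kappa = (0.824 − 0.595)/(1 − 0.595) = 0.56, large-sample 95% CI 0.16 to 0.97.

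Now place the 3 discordant patients. Let b be the patients in the stratum whom Ga alone classifies correctly, c those whom FDG alone does, and n the stratum size. The difference is (b − c)/n. The Tango limits are the values d at which |b − c − nd| / √{n[2q + d(1 − d)]} = 1.96, where q is the constrained estimate of the probability that FDG alone is correct.

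- *All 3 aseptic.* Sensitivity 9/9 and 9/9. Specificity Ga 6/8, FDG 3/8. b = 3, c = 0, n = 8: +38 points (95% CI −7 to 69).
- *All 3 infected.* Sensitivity Ga 6/9, FDG 9/9. Specificity 3/8 and 3/8. b = 0, c = 3, n = 9: −33 points (95% CI −65 to 7).

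Kappa and its interval are identical in the two cases; the conclusions about Ga are opposite.

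**3. What can 17 patients show?** The exact two-sided McNemar p for b discordant patients all in one direction is 2×0.5^b: 0.25 for 3, 0.125 for 4, 0.0625 for 5, 0.031 for 6. So p < 0.05 needs at least 6 discordant patients in a stratum. With 6 to 8, all must favour one tracer (7-1 gives 0.070); 8-1 gives 0.039. With no discordant patient at all, the Tango interval is still ±32 points at n = 8 and ±30 at n = 9.

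Illustrative power for specificity takes Ga 0.76 from the osteomyelitis/diskitis study in Preliminary Studies, with FDG 0.40 to 0.60 and independent or nested errors assumed. It is under 0.1% to 11% with 8 or 9 aseptic patients. Other assumed discordance (50% favouring Ga, 5% favouring FDG) gives 19.6% with 9 and 42.0% with 12. These are illustrations, not bounds.

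**4. Predictive values.** In the first case PPV is 9/11 for Ga and 9/14 for FDG. The denominators are different sets of patients, so McNemar does not apply.

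**The case against.** The strongest reply is that the analysis is there and only its label is missing. Much of that stands. Both documents commit to comparing sensitivity and specificity as separate measures against the gold standard, and the classification bullet supplies everything needed for the paired tables. A reader might infer that the plan omits the Ga-FDG accuracy comparison altogether. The documents do not support that: the comparison is promised four times, and what is missing is its method and interval.

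A reader might also infer that a McNemar test pooled over all 17 patients would be as blind as kappa. That holds only if results are scored positive or negative. The bullet before McNemar classifies results as true or false, so correct or incorrect is the natural reading. The pooled count is then 3-0 for Ga in the first case and 0-3 in the second: the p-value is 0.25 both times, but the direction differs.

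The MRI/CT comparison is not pointless either. Protocol section 3 (Potential for Benefit) argues that available modalities in general, FDG among them, discriminate poorly. And the McNemar bullet may be loose drafting that was meant to include Ga against FDG. Neither document says so, and under that reading it still gives no difference, interval or separation by reference status.

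Finally, the analysis is primarily descriptive. That is a reason to put the interval ahead of the p-value. It does not excuse leaving out the interval.

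**Conclusion.** The concern holds as a gap in specification. As worded, neither document names a paired difference, interval or test for the Ga-FDG accuracy comparison, and the only paired categorical test points at chart-derived MRI and CT. Kappa cannot fill the gap: the same value, 0.56, fits a 38-point gain in specificity and a 33-point loss in sensitivity. The figures assume a 9/8 split and a chosen cross-table; the conclusion about wording does not depend on them.

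Leaving the method open creates a risk that it is chosen after the data are seen; nothing shows that this happened or was intended. Nor do the power illustrations prove that the study must fail, since FDG specificity and the case split are assumed. They support only the statement that 17 patients allow estimation with wide intervals. The point should be fixed, and the cost is small.

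**What to change.** In Protocol section 4 and the SAP, replace the McNemar bullet with:

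> Per patient, Ga and FDG will be compared with each other, separately in reference-positive patients (sensitivity) and reference-negative patients (specificity). The main result is each paired difference with a 95% CI suited to small paired samples (e.g. Tango score), with the exact McNemar p-value as supporting. Each sensitivity, specificity, PPV and NPV will have an exact 95% CI; PPV and NPV will be compared descriptively, not by McNemar. Comparison of each tracer with MRI and with diagnostic CT is secondary, in patients who have that scan, with the number reported.

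Add:

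> In a stratum, p < 0.05 needs at least 6 discordant patients. With 17 patients the comparison is mainly estimation, and a non-significant result is not evidence of equivalence.

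Two details need a sentence each. The 2.0 target-to-background rule scores a region of interest, so the plan should say how regions combine into one result per patient. The Tango interval and the exact test can also disagree: 4-0 among 8 patients gives an interval of 1 to 79 points but p = 0.125. The plan should say in advance that any claim of significance rests on the exact test.

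The cost is wording in two documents, with no new scans or data. The expectation of superiority can stay, but it will rest on an estimate with a wide interval, and the MRI/CT comparison becomes secondary.

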#### ***Exclusion Criteria:***

- Pregnant or breast-feeding women.
- Inability to consent.
- Known or suspected hypersensitivity to metals or gallium.
- Drainage from the joint
- Active inflammatory/infectious process at any location other than prosthetic joint.
- History of HIV, lupus, rheumatoid arthritis and neutropenia

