For each subject, we will record the presence and location of abnormal uptake. For the PET/CT images, we will generate a region-of-interest (ROI) around each area of morphologic abnormality to calculate a mean standardized uptake value (SUV), a maximum SUV, and a target-to-background ratio. A target-to-background ratio of at least 2.0 will be used to score a particular ROI as positive. These values will be compared quantitatively with those of contralateral normal joint. Radiotracer uptake pattern on each modality will be classified according to known methods. Then, we will descriptively and quantitatively correlate Ga-citrate PET/CT findings with those of F-FDG PET/CT. Using the macroscopic intraoperative and later tissue histology and culture as the gold standard, sensitivity, specificity, and positive and negative predictive values of Ga and FDG PET will be calculated and compared with each other. We will also review the PET/CT images for multifocal involvement, if any.

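### Run on a lesion basis, the Ga versus FDG t-test treats lesions from one patient as independent, and the plan gives neither a cluster method nor a rule for one value per patient.

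*Protocol*

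**What the plan says.** Both documents record mean SUV, maximum SUV and a target-to-background ratio for each region of interest. Protocol section 4 says "we will generate a region-of-interest (ROI) around each area of morphologic abnormality", and adds: "We will also review the PET/CT images for multifocal involvement, if any". The Imaging Protocol in section 3 gives a search for further foci as one reason for scanning the whole body. The SAP repeats the section 4 text.

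The Statistical Analysis bullets, the same in both documents, then state: "The student t-test will be used to statistically compare the quantitative findings of 68 Ga-citrate and 18 F-FDG scans". They also state: "Analysis will be done on a lesion basis and on a patient basis", with P below 0.05 as significant. Neither document says whether the t-test is paired, which of the three measures it uses, how several lesions become one patient value, or how lesions within a patient are handled.

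Uptake meets the reference standard in categorical form: "A target-to-background ratio of at least 2.0 will be used to score a particular ROI as positive", after which "sensitivity, specificity, and positive and negative predictive values of Ga and FDG PET will be calculated and compared with each other". An uptake-pattern classification is also planned. The Exclusion Criteria limit disease elsewhere by excluding: "Active inflammatory/infectious process at any location other than prosthetic joint".

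**The concern.** Two lesions around one prosthesis share the patient, the tracer injections and usually the disease process, so their Ga minus FDG differences are likely to be alike. Pairing the tracers within a lesion does not remove that likeness. A t-test that counts each lesion as a separate observation then understates its standard error, giving intervals that are too narrow and P values below 0.05 more often than 5% of the time. This is a pilot whose results are meant to support larger studies, so the precision reported for the Ga-FDG difference matters even if nobody acts on the P value.

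A lesser matter sits beside it. The t-test serves the uptake aim in section 3. The aim of telling infection from aseptic loosening is served by sensitivity, specificity and predictive values. The continuous SUVs are not related to infection status at all, and the ratio only after the cut at 2.0.

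**Working it through.** **Inputs.** From the documents: 17 patients, Student t-test, alpha 0.05 (two-sided assumed), analysis by lesion and by patient. Not given, so assumed: lesions per patient (one to three) and the intraclass correlation (ICC) of the lesion-level Ga minus FDG difference (0.3 to 0.7). The plan states no figure on this point that could be reproduced.

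**Step 1: variance inflation.** With m_i lesions in patient i and N lesions in total, the variance of the lesion mean exceeds its independent-data value by

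V = 1 + ICC × Σm_i(m_i − 1) / N,

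and the true type I error is about 2 × [1 − Φ(1.96/√V)]. For six patients with two lesions, N = 11 + 12 = 23 and Σm_i(m_i − 1) = 6 × 2 = 12. At ICC 0.7, V = 1 + 0.7 × 12/23 = 1.37, so 1.96/√V = 1.68 and the type I error is about 9.3%.

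**Step 2: formula and simulation, paired lesion-level test** (each pair of figures is for ICC 0.3 / 0.7)

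| Lesion pattern, 17 patients | N | Σm(m−1) | V | Formula | Simulated |
|---|---|---|---|---|---|
| One each | 17 | 0 | 1.00 / 1.00 | 5.0% / 5.0% | about 5% |
| One patient with two | 18 | 2 | 1.03 / 1.08 | 5.4% / 5.9% | 5.3% to 5.9% |
| Two patients with two | 19 | 4 | 1.06 / 1.15 | 5.7% / 6.7% | 5.8% / 6.8% |
| Six patients with two | 23 | 12 | 1.16 / 1.37 | 6.8% / 9.3% | 7.0% / 9.5% |
| All with two | 34 | 34 | 1.30 / 1.70 | 8.6% / 13.3% | 8.6% / 13.6% |
| All with three | 51 | 102 | 1.60 / 2.40 | 12.1% / 20.6% | 12.2% / 21.3% |

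**Step 3: effect of pairing.** If the lesion-level test is unpaired, a Ga-FDG correlation of 0.3 to 0.7 works the other way: with all patients having two or three lesions, simulated type I error runs from 0.3% to 14%. With one value per patient and a correlation of 0.5, the unpaired test has type I error 0.8% and power 23% for a 0.5 SD difference; the paired test has 5.0% and 49%.

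**Step 4: remedies.** In the same simulations, a paired t-test on patient means gives 4.8% to 5.1%. A random patient effect with t on 17 − 1 = 16 degrees of freedom gives 4.5% to 5.6%. A plain percentile bootstrap of patients gives 7.5% to 8.6%, too high to rely on with 17 patients.

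**Step 5: the continuous values.** The t-test compares uptake level, not discrimination. In a simulated 17 patients (8 infected, correlation 0.5), equal AUCs of 0.86 with FDG shifted up by 1 SD made the paired t-test significant in 97% of trials. Ga AUC 0.96 against FDG AUC 0.50 with equal overall means made it significant in 0.2%.

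For the common cut-off, assume normal ratios, an infected-aseptic gap of 1.5 SD for both tracers (AUC = Φ(1.5/√2) = 0.86) and a cut at the Ga midpoint of 0.75 SD. Ga sensitivity and specificity are both Φ(0.75) = 77%. With FDG shifted up by 0.5 SD they are Φ(1.25) = 89% and Φ(0.25) = 60%; with 1.0 SD, Φ(1.75) = 96% and Φ(−0.25) = 40%. FDG loses specificity and gains sensitivity, and the plan reports both.

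**The case against.** The strongest reply is that the problem may hardly arise. Patients enter for one painful prosthesis, active disease elsewhere is excluded, and a patient-basis analysis is already planned. With one lesion each there is no inflation; with one two-lesion patient it is under one percentage point. The top figure of 21% needs three lesions in all 17 patients at an ICC of 0.7. All of this stands and limits the size. It does not fill the gap: a lesion-basis analysis is planned, multiple foci are foreseen, and the patient-basis analysis has no rule for forming its value.

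A reader might infer that the t-test is wrongly unpaired. The text does not show that; a Student t-test includes the paired form, so this needs clarifying and is not a demonstrated error.

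A reader might also infer that uptake is never related to infection, or that the common cut-off would wrongly favour Ga. The first fails because the ratio reaches infection status through the 2.0 cut. On the second, in the Step 5 scenario sample specificity alone favours Ga in 73% to 99% of trials, but Ga has higher specificity with no lower sensitivity in only 20% to 36%. The uniform FDG shift is hypothetical, and the documents do not say whether the ratio or the uptake pattern decides a patient's result.

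**Conclusion.** The point holds for the lesion-basis t-test. As written, it treats lesions within a patient as independent and no remedy is stated. The omission is certain from the text; its size is not. Under ICCs of 0.3 to 0.7, type I error of the paired test runs from about 5% to 6% (one two-lesion patient) through 7% to 10% (six) and 9% to 14% (all with two) to at most 21% (all with three). It is 5% with single lesions. The direction depends on pairing, since an unpaired test may be conservative, so a firm claim of excess false positives would go beyond the documents. It should be fixed because the repair is cheap.

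Relating the continuous SUVs and ratios to infection status is an optional supplement, not the correction of an error. Nor would an AUC comparison settle whether a tracer difference reflects uptake level or discrimination: with equal discrimination, the observed AUC difference exceeds 0.10 in about 20% to 40% of simulated trials of 17.

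**What to change.** In the Statistical Analysis bullets of both documents:

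1. Name one quantitative measure, for example the target-to-background ratio, and compare Ga with FDG by a paired patient-level test with a 95% CI, using the patient mean when there are several regions. State that this addresses uptake, not accuracy.
2. For lesion-basis analyses of these values, use a random patient effect with t on patients minus 1 degrees of freedom, or patient means. Report the number of lesions per patient.
3. Optional, labelled exploratory: for each tracer, report maximum SUV and ratio by reference diagnosis, and the paired AUC difference with a patient-level 95% CI. State that with 17 patients this is descriptive. The AUC-difference half-width is about 0.2 to 0.3 (assuming AUCs of 0.85 and 0.70, 4 to 8 infected, correlation 0.3 to 0.7), and coverage is approximate. State also that it cannot by itself separate a shift in uptake level from a difference in discrimination, and that it supplements the planned sensitivity and specificity comparison.

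The cost is wording and a little extra analysis of data already to be recorded, with no new patients or scans. The drawback is wide intervals.
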